3.2. Duration of the Study

It is estimated that the patient recruitment will be completed approximately in 24 months.

All patients included will receive study therapy until radiographic or symptomatic progression, unacceptable toxicity or withdraw of the informed consent, whatever occurs first, this is the active treatment phase. Patients discontinuing the study treatment will enter the follow-up phase.

For safety reasons all patients will have a visit 30 (+/-7) days after finishing treatment with the study drugs/medications. This post-treatment visit must be performed before starting with any new anticancer therapy; however, in case the beginning of this new therapy cannot be delayed as per the investigator's judgment, the safety visit may be performed in advance, but always before starting with the new anticancer therapy.

All patients will be followed till death or data cut-off date to evaluate the OS objective.

The start date of study is the date of the first site initiation visit. The data cut-off date will be the date of last patient's death or withdraw of the informed consent or the date when there is sufficient data to achieve the primary and secondary objectives, whichever comes first. It is estimated that the final analysis could be performed approximately 30 months after the enrolment of the first patient because, considering a median OS of 12 months, it is estimated that more than 50% of death events will have occurred at that time and overall survival analysis could be performed.

The study will be considered complete following the data cut-off date and data-lock for the final analysis. Performing exploratory objectives will be independent of the date of the end of the study.

4. Study Population

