6.1.2. Secondary Efficacy Assessments

Secondary efficacy assessments are PFS, CBR, RD, and OS:

- ✓ Progression Free Survival (PFS): is defined as the time from study enrolment to the first documented progressive disease, using RECIST version 1.1., or death from any cause, whichever occurs first.
- ✓ Clinical Benefit Rate (CBR): is defined as complete response (CR), partial response (PR), or stable disease (SD) ≥ 24 weeks according to the RECIST version 1.1.
- ✓ Response Duration (RD): is defined as the time from the first documentation of objective tumour response (CR or PR) to the first documented progressive disease using RECIST version 1.1, or to death due to any cause, whichever occurs first.
- ✓ Overall Survival (OS): is defined as the time from the date of study enrolment to the date of death from any cause.

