m	
Disease assessment for all patients at baseline will include:
 
 • CT or MRI scan of the chest, abdomen and pelvis (CAP). • Bone scans will be mandatory if the patient has bone disease or if there is any suspicious of bone metastases. Any suspicious abnormalities (ie, hotspots) identified on the bone scans at baseline must be confirmed by X-ray, CT scan with bone windows or MRI. Bone lesions identified at baseline will follow the same assessment schedule as for measurable lesions. • Brain CT or MRI scan is mandatory if the patient has CNS metastases or if there is any suspicious of CNS metastases. • CT or MRI scan of any other sites of disease as clinically indicated. • Clinical assessment of superficial disease which will include photographs of all superficial metastatic lesions. 
All lesion measurements must be recorded in the eCRF. Tumour response will be assessed using RECIST v.1.1. every 8 weeks (+/- 1 week).

n	Bone scans (if applicable) will be repeated if indicated when complete response is identified in target disease or when progression in bone is suspected. Responses should be confirmed according to RECIST v.1.1 after at least 28 days.
r	Only to be performed post-study treatment if disease progression has not yet been confirmed and patients have not begun a new therapy, the tumour assessment will be performed every 8 weeks from the last tumour assessment.
s	The patients will be followed for survival until death, loss to follow-up, withdrawal of consent or study termination by GEICAM. After progression or patient is receiving other therapy, the tumour assessment will be performed according to the standard medical practice. The date of death and all treatments received by the patient after progression (according to the standard medical practice) will be collected in the eCRF.
t	At least one paraffin sample from a metastatic lesion must be sent to the sponsor-designated central laboratory to perform methylation testing and other biomarker analysis related to secondary and exploratory objectives. It is strongly recommended that the metastatic sample has been obtained after previous therapy regimen. Surgery blocks or core biopsies would be acceptable, minimal amount of tumour tissue will be specified in the SMM.

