### Figure 1 Study Design

Potential eligible patients will be screened to assess germinal (g) *BRCA* mutational status at Myriad laboratory (unless the *BRCA* mutational status is already known based on a Myriad previous report).

Blood samples for mutational *BRCA* screening could be sent either 1) during the previous line of treatment, once the eligibility criteria have been reviewed and the patient is considered a potential candidate for the study (at least the patient must have measurable and biopsiable disease) or 2)

after end of the line of treatment prior to study enrolment (simultaneously to the shipment of the tumour samples for methylation analysis). A specific Informed Consent Form (ICF) must be signed for this screening assessment.

Somatic (s) *BRCA* promoter methylation will be assessed also centrally at an external reference central laboratory selected by GEICAM. Tumour samples must proceed from a metastatic lesion, it is strongly recommended to obtain it after the line treatment immediately previous to the study entry.

Patients with a positive methylation status on *BRCA1* and/or *BRCA2* and lacking of known deleterious or suspected deleterious mutations in both genes could be included in the study to receive olaparib tablet formulation at 600 mg daily dose (given in two oral administrations of 300 mg every 12 hours approximately). Blood and tumour samples collected from all registered patients could be used for the secondary and exploratory analyses of the study, including but not limited to the assessment of germline methylation status and gene expression levels of *BRCA1/2*.

Patients will continue to receive their treatment until objective disease progression, symptomatic deterioration, unacceptable toxicity, death or withdrawal of consent, whichever occurs first.

Each assessment of tumour response will be performed as scheduled according to the calendar regardless of any dosing delay to prevent the introduction of bias into the assessment of efficacy.

According to RECIST v.1.1 in case of patients with a global deterioration of health status requiring discontinuation of treatment without objective evidence of disease progression at that time every effort should be made to document objective progression, even after discontinuation of treatment.

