#### **9.2.1.2 Analysis of Secondary Endpoints**

The secondary efficacy endpoints are:

**Clinical Benefit Rate (CBR):** A patient will be considered to have CB if the patient has a sustained complete response (CR) or partial response (PR), or stable disease (SD)  $\geq 24$  weeks according to RECIST version 1.1 definitions. Otherwise, the patient will be considered as not achieving CB in the CBR analysis.

CBR will be estimated by dividing the number of patients with CR, PR, or SD  $\geq 24$  weeks by the efficacy population.

$$\text{Clinical Benefit Rate} = \frac{\text{Number of CRs + PRs + SD} \geq 24 \text{ weeks}}{\text{Efficacy Population}}$$

The CBR will be reported, including a 95% confidence interval.

For the CBR analysis in the ITT population, patients with inadequate data for tumour assessment (e.g., no baseline assessment or no follow-up assessments) will be considered as not achieving CB in the CBR analysis.

**Duration of Response (DoR):** DoR is defined as the time from the first documentation of objective tumour response (CR or PR) to the first documented PD using RECIST version 1.1, or to death due to any cause, whichever occurs first. DoR data will be censored on the date of the last tumour assessment on study for patients who do not have objective PD and who have not died due to any cause while on study. Additionally, patients who start a new anti-cancer therapy prior to documented PD will be censored at the date of the last tumour assessment prior to the start of the new therapy.

RD will only be calculated for the subgroup of patients with an objective response.

**Progression-Free survival (PFS):** PFS is defined as the time from study enrolment to the first documented PD, using RECIST version 1.1, or death from any cause, whichever occurs first. PFS data will be censored on the date of the last tumour assessment on study for patients who do not have objective PD and who have not died due to any cause while on study. Additionally, patients who start a new anti-cancer therapy prior to documented PD will be censored at the date of the last tumour assessment prior to the start of the new therapy.

The analyses of PFS will be performed in the ITT and Efficacy populations. PFS time will be summarized for the ITT population using the Life tables and displayed graphically where appropriate. Confidence intervals (CIs) for the 25th, 50th and 75th percentiles of the event free time will be reported.

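### PFS and duration of response are censored at the last scan when a patient starts a new anticancer therapy before RECIST progression, so clinical failures who switch before a confirming scan push the estimates upward, and no sensitivity analysis tests this

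*SAP*

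**What the plan says.** **Event.** SAP 9.2.1.2: "PFS is defined as the time from study enrolment to the first documented PD, using RECIST version 1.1, or death from any cause". Protocol 6.1.2 gives the same events for PFS and for response duration. Symptomatic progression is not among them.

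**Censoring.** SAP 9.2.1.2: "PFS data will be censored on the date of the last tumour assessment on study for patients who do not have objective PD". This applies only if no death occurred on study. A further rule, for both PFS and DoR, is that "patients who start a new anti-cancer therapy prior to documented PD will be censored at the date of the last tumour assessment" before the new therapy. Protocol 8.2.6.2 has the same rules.

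**Stopping treatment.** Protocol 3.2: "All patients included will receive study therapy until radiographic or symptomatic progression, unacceptable toxicity or withdraw of the informed consent". SAP section 3 also lists symptomatic deterioration: "Patients will continue to receive their treatment until objective disease progression, symptomatic deterioration, unacceptable toxicity, death or withdrawal of consent".

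**Scans after stopping.** Protocol Attachment 1, footnote r, keeps 8-weekly assessments going after treatment, with this limit: "Only to be performed post-study treatment if disease progression has not yet been confirmed and patients have not begun a new therapy". Footnote s leaves imaging after a new therapy to standard practice. Protocol 3.1 and 6.1 and SAP section 3 ask sites to try hard to document objective progression after a patient stops for global deterioration.

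**Sensitivity analyses.** Protocol 8.2.6.2 defers additional sensitivity analyses of the secondary endpoints to the SAP. The SAP analyses PFS in the Efficacy and ITT populations (Tables 2.2.1 and 2.2.2) under one censoring rule and gives no alternative to it.

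**The concern.** Kaplan-Meier treats a censored patient as having the same future risk as those still under observation. That is doubtful for someone who stopped olaparib because of symptoms of progression and needed the next line before a scan could confirm it. Such a patient leaves the risk set at the previous scan, as if still doing well. Because protocol scans end at the switch, the progression is unlikely to be recorded on schedule. The rule also discards a later death, although the definition says "or death from any cause, whichever occurs first".

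This rule differs from the one in Protocol 3.1 for deteriorating patients in whom no assessment can be done. It also covers patients who could have been scanned.

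The trial has one arm, so no control group shares the distortion. Progression is assessed locally and the timing of a switch is a clinical decision. Readers will naturally set the PFS result beside the short medians quoted in Protocol Table 4 (54 days and 3.68 months for two olaparib breast cohorts), although the plan makes no formal comparison.

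**Working it through.** **Plan's own figure.** There is none to reproduce. The documents state no PFS assumption, event target or power; the design figures (31 evaluable, 34 enrolled) rest on the response rate.

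**Inputs from the documents**
- Scan interval: 8 weeks (Protocol 6.1.1).
- Illustrative true median PFS: 3.68 months (Protocol Table 4), that is 3.68 × 30.4375 / 7 = 16.0 weeks. As a range: 54 days (7.7 weeks, Table 4) to 7.0 months (30.4 weeks, Protocol 1.4.5.1).
- Evaluable patients: 31.

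**Assumptions**
- Failure times are exponential.
- A share q of failures is symptomatic, moves to new therapy before the next scan, and is censored at the previous scan. The documents do not give q; it is varied from 10 to 30%.

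**Formulas**
- Failure probability per 8-week interval: h = 1 − 2^(−8/median).
- If all failures count, the interval hazard is h.
- Under the planned rule, the share qh leaves the risk set at the start of the interval and only (1 − q)h are events, so the hazard is h′ = h(1 − q)/(1 − qh).
- 24-week PFS is (1 − hazard)³. The smoothed median is 8 ln 2 / [−ln(1 − hazard)].

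**Results at a 16.0-week median.** h = 1 − 2^(−8/16.0) = 0.293. With all failures counted, 24-week PFS is 0.707³ = 35.4%.

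| q | h′ | 24-week PFS, planned rule | Smoothed median |
|---|---|---|---|
| 0% | 0.293 | 35.4% | 16.0 weeks |
| 10% | 0.272 | 38.7% | 17.5 weeks |
| 20% | 0.249 | 42.4% | 19.4 weeks |
| 30% | 0.225 | 46.6% | 21.8 weeks |

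For q = 20%: h′ = 0.293 × 0.80 / (1 − 0.20 × 0.293) = 0.2343/0.9414 = 0.249, and 0.751³ = 42.4%.

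**Against sampling error.** With 31 patients, the standard error (SE) of the 24-week estimate is √(0.354 × 0.646/31) = 8.6 points. The shifts of 3.3, 7.0 and 11.2 points are about 0.4, 0.8 and 1.3 SE.

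**Other medians.** The relative rise in the smoothed median is similar: 8–10% at q = 10%, 18–23% at 20% and 30–39% at 30%, over true medians of 54 days to 7.0 months.

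**Simulation check.** With 31 patients and 6 to 30 months of follow-up, mean 24-week PFS is 38.4, 42.4 and 46.6% at q = 10, 20 and 30%, against about 35%. On average 2.8, 5.7 and 8.5 events become censorings. When switches are made unrelated to failure, the figures are 35.2% and 35.3%: no bias.

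**If a scan can fall before the switch.** Assume a 30-day gap between stopping and new therapy, and that a scan in the gap shows progression. A scan then falls in the gap in 30/56 = 54% of cases, so the affected share drops to q × 26/56. For q = 10, 20 and 30% that is 4.6, 9.3 and 13.9%, and the same formula gives 24-week PFS of 36.8, 38.4 and 40.1%.

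**The case against.** The strongest reply is that the plan already limits the problem. Scans do not stop with olaparib: footnote r continues them, and sites are told to pursue objective progression. The post-treatment visit is set at 30 (±7) days and before any new therapy, which leaves room for a scan. Only patients who switch before that scan are affected. This stands, and it roughly halves the effect in the last calculation. It does not remove it, because Protocol 3.2 allows the visit to be brought forward when new therapy cannot wait, and those are the patients most likely to be failing.

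Second, the affected share is undocumented, and at 10% the shift is below half an SE. This also stands. A reader might infer that PFS is certainly biased upward, or that scanning ends when treatment stops. The documents support neither.

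Third, a reader looking at raw Kaplan-Meier medians might infer a jump from 16 to 24 weeks. That is largely an effect of the 8-week scan grid; the smoothed medians are the fair measure.

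Fourth, PFS and DoR are secondary single-arm estimates with no threshold, and discontinuation reasons and subsequent therapies are already to be tabulated. This limits the importance. Those tables do not show how far the PFS estimate depends on the rule.

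**Conclusion.** The point holds in a conditional form. The censoring rule is explicit, it applies to both PFS and DoR, and it treats clinical failures who switch before a confirming scan as uninformative. Any bias from those patients is upward. At a 16-week median it is about 3 to 11 percentage points on 24-week PFS if 10–30% of failures take this path with no scan in between, about 1 to 5 points if a 30-day gap lets a scan intervene, and zero if switches are unrelated to failure. These figures rest on exponential failure times and an assumed share. The same logic applies to DoR, but its size was not calculated.

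The response rate, the Simon decision and overall survival are unaffected. The planned rule may remain the main analysis. What is missing is a prespecified check on it, of the kind the protocol leaves to the SAP.

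**What to change.** Keep the planned rule as the main analysis. Add to SAP 9.2.1.2 and to Table 2.2 one prespecified sensitivity analysis for PFS and DoR. In it, discontinuation for symptomatic progression or deterioration, or start of a new anticancer therapy before RECIST progression, counts as an event at the earlier of those dates. Report the number censored for new therapy under the main rule, by reason for the switch. The table list in SAP section 10 has no DoR table, so the DoR version needs its own entry.

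Two things to avoid:
- Do not follow patients who switch for toxicity to death as if progression-free. With protocol scans ended, this could raise PFS.
- Do not present the two analyses as limits on true PFS. They measure different things.

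The cost is SAP wording and one extra run. Discontinuations (Protocol 4.4.1) and details of, and reasons for, subsequent therapy (Protocol 5.5.4) are already collected; the sponsor should confirm that the eCRF separates symptomatic from RECIST progression. The downside is a second PFS figure that is likely to be less favourable and that mixes clinical failure or change of treatment with RECIST progression.

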## 9.2.2 Safety Analyses

The toxicity and tolerability of study drugs/medications will be evaluated in the safety population.

Safety analyses will include summaries of the incidence of adverse events (AEs) by maximum NCI-

CTCAE grade (v4.0; NCI 2010) that occur during the study treatment period or within 30 days of the last dose of study treatment, regardless of causality and according to the relationship to study drug/medication as assessed by the Investigator. Additionally, the following safety-related outcomes will be summarized:

- Study treatment discontinuations due to AEs.
- Deaths.
- SAEs and AESIs.
- Hospitalizations and transfusions.
- Use of key concomitant medications or growth factors.

Analyses for data with discrete dates, for example, deaths, transfusions, and concomitant medications, will be done through 30 days after each patient's last dose of study treatment. Adverse events will also be analysed in this timeframe; that is, if an event starts within 30 days of discontinuation from study treatment, but after 30 days after the last dose of study treatment, it will not be included.

Adverse events and SAEs data will be presented in frequency tables by grade. Haematological and clinical biochemistry toxicities will be assessed from laboratory test parameters. The safety analyses will be performed in the safety population.

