1.4.5.2. Olaparib 300 mg b.i.d. monotherapy (tablet formulation) pooled dataset

This section presents a pooled analysis of olaparib 300 mg b.i.d. (tablet formulation) monotherapy safety data from Study D0816C00002 (including the China cohort) plus 10 additional studies: D0819C00003 (OlympiAD), D0810C00024, D0816C00004, D0816C00007, D0816C00008, D081BC00001, D081CC00001, D0816C00006, D0816C00005 and D081BC00002. A total of 759 patients with advanced solid tumours are included in this analysis.

In the olaparib 300 mg b.i.d. tablet pool dataset, the contributing studies have differing patient populations. The majority of patients in the pooled dataset had either ovarian fallopian tube or primary peritoneal cancer (335/759) or breast cancer (268/759). Patients with other solid tumours including colon/colorectal (n=23), pancreas (n=12) or prostate (n=11) were also treated. Patients were generally heavily pre-treated with anticancer therapies.

The number of patients in the 300 mg b.i.d. monotherapy tablet pool dataset who had at least 1 AE in any category during the course of the study is 741 (97.6 %), any AE causally related to study drug 654 (86.2 %), any AE of CTCAE Grade 3 or higher 278 (36. 6 %), and any AE leading to discontinuation of study treatment 50 (6.6%).

Haematological toxicity was reported at an increased frequency with the tablet formulation, compared with the capsule formulation; however, anaemia and neutropenia remained manageable by interrupting or reducing the olaparib dose or giving blood transfusions or colony stimulating factor, when indicated; treatment discontinuation was rarely required. Reports of thrombocytopenia remained at low frequency with the tablet formulation; these events were primarily low grade and rarely required treatment discontinuation.

Anaemia, neutropenia and fatigue were the most common CTCAE Grade 3/4 AEs in the tablet pool dataset: CTCAE Grade 3/4 anaemia was reported by 14.6% of patients, CTCAE

Grade 3/4 neutropenia was reported by 3.8% of patients and CTCAE Grade 3/4 fatigue was reported by 3.2% of patients.

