8.2.7. Safety Analyses

The toxicity and tolerability of study drugs/medications will be evaluated in the safety population. Safety analyses will include summaries of the incidence of adverse events by maximum NCI-CTCAE grade (v4.0; NCI 2010) that occur during the study treatment period or within 30 days of the last dose of study treatment, regardless of causality and according to the relationship to study drug/medication as assessed by the Investigator. Additionally, the following safety-related outcomes will be summarized:

- Study treatment discontinuations due to adverse events.
- Deaths.
- SAEs and AESIs
- Hospitalizations and transfusions.
- Use of key concomitant medications or growth factors.

Analyses for data with discrete dates, for example, deaths, transfusions, and concomitant medications, will be done through 30 days after each patient's last dose of study treatment. Adverse events will also be analysed in this timeframe; that is, if an event starts within 30 days of discontinuation from study treatment, but after 30 days after the last dose of study treatment, it will not be included.

Adverse events data and serious adverse events will be presented in frequency tables by grade. Haematological and clinical biochemistry toxicities will be assessed from laboratory test parameters. The safety analysis will be performed in the safety population.

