Events to Collect	AE/SAEs Related to Procedures	New/Ongoing AE/SAEs Regardless of Relatedness to Study Treatment or Procedures		
New/Ongoing SAEs, including sudden death of unknown cause, that the investigators considers there is a reasonable possibility that the event is causally related to the investigational product or protocol procedure, even if the study has been closed
 
Any case of MDS/AML or new primary malignancy whether it is considered a non-serious AE [e.g. non-melanoma skin cancer] or SAE, and regardless of investigator's assessment of causality

Abbreviations: AE = adverse event, ICD = informed consent document, SAE = serious adverse event.

Protocol Attachment 5. Actions required in cases of combined increase of Aminotransferase and Total Bilirubin – Hy's Law

TABLE OF CONTENTS

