	3.1.4	Grade 3 or Higher Treatment-Emergent Adverse Events by System Organ Class and Preferred Term
	3.1.5	Grade 3 or Higher Drug-Related Treatment-Emergent Adverse Events by System Organ Class and Preferred Term
	3.1.6	Most common (at least 10% in any treatment arm) Treatment-Emergent Adverse Events by Preferred Term
	3.1.7	Serious Treatment-Emergent Adverse Events by System Organ Class and Preferred Term Safety Population

	3.1.8	Serious Drug-Related Treatment-Emergent Adverse Events by System Organ Class and Preferred Term Safety Population
	3.1.9	Treatment-Emergent Adverse Events by Grade
	3.1.10	Drug-Related Treatment-Emergent Adverse Events by Grade
	3.1.11	Serious Treatment-Emergent Adverse Events by Grade
	3.1.12	Adverse Events from Laboratory according NCI CTC v4.03 by System Organ Class and Preferred Term
3.1.	Deaths	
	3.2.1	All-Cause Mortality Safety Population
4	OTHER ENDPOINTS	
	4.1	Changes of germline methylation pre and post treatment
	4.2	Correlation between germline methylation status and efficacy outcome data
	4.3	Correlation between germline methylation status and somatic methylation status
	4.4	Correlation of methylation between primary and metastatic lesions
	4.5	Correlation between expression data and promoter methylation status of BRCA1/2 and outcome data
5	EXPLORATORY OBJECTIVES (if performed)	
	5.1	Exploratory biomarkers of response or resistance to Olaparib
	5.2	Review potential pharmacogenomics analyses related to drug response or adverse drug reactions
	5.3	Specific mutations or epigenetic biomarkers identified in pre-therapy tumour specimens as potentially linked to treatment response

*The numbers of tables and figures do not have to match exactly with those of the statistical report. The feasibility and interest of performing some of the described tables and figures based on the available number of patients, data and biological samples.*

*Please see Shells Tables, Listings and Figures.*

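### The 30-day safety window has no cut at the start of a new anticancer therapy, so some post-switch events can be summarised as outcomes on olaparib

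*SAP*

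**What the plan says.** **Analysis window.** SAP 9.2.2 counts AEs "that occur during the study treatment period or within 30 days of the last dose of study treatment, regardless of causality". Protocol 8.2.7 has the same rule and adds: "Analyses for data with discrete dates, for example, deaths, transfusions, and concomitant medications, will be done through 30 days after each" patient's last dose. Hospitalizations and transfusions are listed safety outcomes, as is "Use of key concomitant medications or growth factors". AEs are also to be summarised "and according to the relationship to study drug/medication as assessed by the Investigator", and SAP section 10 plans tables such as "Drug-Related Treatment-Emergent Adverse Events by Grade".

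**New therapy inside the window.** Protocol 3.2 makes it the default that the post-treatment visit (day 30, plus or minus 7) comes before any new anticancer therapy. If the investigator judges that the therapy cannot wait, "the safety visit may be performed in advance, but always before starting with the new anticancer therapy". Protocol 6.2.1 and the notes to Attachment 1 repeat this.

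**Collection.** Attachment 4 has one entry for the on-treatment and 30-day post-treatment columns: "New/Ongoing AE/SAEs Regardless of Relatedness to Study Treatment or Procedures". Protocol 6.2.4 (SAEs and AESIs) and 5.5 (concomitant medication) also run to about 30 days after the last dose. Attachment 1, footnote l, instead ties AE recording to the post-treatment visit.

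**The concern.** The protocol allows a second anticancer therapy to begin while the safety window is still open, and the analysis does not react to it. SAP 9.2.1.2 does react for efficacy: PFS and duration of response are censored at the last assessment before a new therapy. Safety has no counterpart, although its window is otherwise defined to the day.

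Olaparib safety is a secondary objective, and there is no control arm against which such a mixture would show. Protocol 1.4.5.2 names anaemia and neutropenia among the most common grade 3/4 events with olaparib tablets. Transfusions and growth factors are used to manage those events, and they may also be given for the effects of a next-line regimen. For transfusions, growth factors, hospitalizations and deaths the plan states no split by causality, so a reader of the report could not separate the two sources.

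**Working it through.** The plan states no figure that depends on this window, so the check is mainly textual.

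**1. Is there a cut at new therapy?** None appears in SAP 9.2.2 or Protocol 8.2.7. Protocol 6.2.3 names another therapy as ending follow-up only for drug-related toxicity that persists beyond 30 days.

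**2. Can new therapy fall inside the window?** Yes, through the exception in Protocol 3.2. In addition, a visit at day 30 − 7 = 23 is on time, so therapy could start in the last week of the window without the exception.

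**3. Which data can be affected?**

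| Data | Collected after an early switch? | Causality split planned? |
|---|---|---|
| SAEs | Yes, by calendar to day 30 (Protocol 6.2.4) | Yes |
| Transfusions, growth factors | Concomitant medication recorded to about day 30 (Protocol 5.5); summarised to day 30 | None stated |
| Hospitalizations | Listed outcome; SAE reporting runs to day 30 | None stated |
| Deaths | Yes, to day 30 | None stated |
| Non-serious AEs | Unclear: Attachment 4 says yes; footnote l may end recording at an early visit | Yes |
| Scheduled laboratory toxicity | No planned draw after the new therapy starts | Largely protected |

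The last row is only largely protected because Protocol 6.2.1 also allows unscheduled tests when clinically indicated.

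**4. Size.** The number of misassigned patients would be N × f × t. Here f is the share who switch inside the window with events still recorded, and t is the chance of the event between the switch and day 30. The documents give neither f nor t, so the product cannot be computed. What can be computed is the effect of k misassigned patients, 100 × k / N. N=34 is the planned enrolment (SAP 3.1). N=12 is roughly the safety population if recruitment stops after step 1 (SAP 8). Both denominators assume that every such patient is dosed. Taking k = 1 to 3 as an assumption:

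| k | N=34 | N=12 |
|---|---|---|
| 1 | 100/34 = 2.9 points | 100/12 = 8.3 points |
| 2 | 5.9 | 16.7 |
| 3 | 8.8 | 25.0 |

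For scale, the 14.6% grade 3/4 anaemia rate in the tablet pool (Protocol 1.4.5.2) corresponds to 0.146 × 34 = 5.0 patients. A patient who already had the same event on olaparib adds nothing to a patient-level rate.

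**The case against.** The strongest reply is that the plan already limits the problem.

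- **Early starts are meant to be exceptional.** Visit before new therapy is the default. A reader might infer that early switching will be common because most patients stop at progression, but the documents give no figure for it. This stands.
- **Haematological laboratory data are where the plan is best protected.** SAP 9.2.2 grades haematological and biochemical toxicity from laboratory values, and the last planned draw precedes the new therapy. Protocol 6.2.2 and 6.2.3 make changes in mandated laboratory values AEs only if they are serious or lead to action on olaparib, and no such action is possible once olaparib has ended. A reader might infer a large inflation of the neutropenia rate against the tablet pool, where "Grade 3/4 neutropenia was reported by 3.8% of patients". The documents do not support that: non-serious next-line neutropenia would mostly not be reported as an AE, and any estimate would rest on two assumed proportions. This stands.
- **Attribution is planned.** A reader might take the all-causality tables to be the whole safety result. They are a principal part of it, but drug-related tables stand beside them. This stands for AEs and SAEs, not for transfusions, growth factors, hospitalizations or deaths.
- **A fixed window is conservative.** Protocol 6.2.3 wants follow-up for delayed toxicity, and a cut could remove late olaparib effects from the main tables. This is a real cost. It is met by showing the later events separately rather than discarding them.

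None of this supplies a rule for SAEs and supportive care recorded after a switch.

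**Conclusion.** The gap is real but limited. The window runs to day 30 with no cut at new therapy, and the protocol allows new therapy inside it. The firm part is SAEs, hospitalizations, transfusions, growth-factor use and deaths. Non-serious AEs are affected only if they are still recorded after an early visit, which the protocol leaves unclear. Scheduled laboratory toxicity and the drug-related AE tables are largely protected.

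The size cannot be stated, because the share of early switchers is not in the documents. Each misassigned patient is worth 2.9 points at N=34 or 8.3 points at N=12, so even one or two would be visible. The primary endpoint is not affected. This is a worthwhile, inexpensive improvement to the safety summaries, not a flaw that undermines the trial.

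**What to change.** 1. In SAP 9.2.2 and Protocol 8.2.7, end the main summary window for AEs, SAEs, hospitalizations, transfusions and growth factors at the earlier of 30 days after the last olaparib dose or the day before the first subsequent anticancer therapy.
2. Present events from the start of that therapy to day 30 separately.
3. Keep AESIs, drug-related SAEs and all deaths to day 30 in the main summary, and flag deaths that follow a new therapy.
4. Reconcile Attachment 1 footnote l with Protocol 5.5, Protocol 6.2.4 and Attachment 4 on whether an early safety visit ends AE recording, so that sites collect the same data.

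**Cost.** Some wording and one date comparison. Subsequent therapies are already collected (Protocol 5.5.4 and Attachment 1 footnote s) and tabulated (SAP section 10, tables 1.9), and the PFS censoring rule already needs the start date. The downside is that delayed olaparib effects that appear after the switch, and are not judged related, move to the separate presentation.
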